The wireless monitor to be used is a wearable wireless vital sign monitor called Current™. The device provides continuous real-time transmission of oxygen saturation, respiration rate, pulse rate, temperature, motion and activity, and posture captured every 2 seconds. It is integrated with the Omron Evolv blood™ pressure cuff to allow automated capture of blood pressure. Physiologic data from the sensor is transmitted via WiFi to a secure cloud storage (hosted by Amazon Web Services). Current™ is fully HIPAA¹ compliant and HITRUST² certified and has received US FDA approval. Physiologic data can then be accessed via a secure password protected mobile phone app or displayed on a monitor for real-time viewing. Pre-defined criteria can be used to program alerts or notifications should vital signs fall outside of the range. These notifications can be received via SMS or a mobile app notification. Notifications can be sent to multiple providers at a time. Providers can also log on or off from the device corresponding to their duty shifts.

To complete Aim 1, we will enroll all willing attending doctors and staff midwives with clinical duties covering the maternity ward, emergency cesarean delivery and postoperative care during the study period to use the wireless physiologic system and receive message alerts. Due to staffing the numbers of clinicians may fluctuate during the enrollment period. We will also enroll 1235 women undergoing emergency cesarean delivery during the study period during intervention blocks to wear a wireless physiologic monitor for 24 hours after birth. An additional 1235 women, also undergoing emergency cesarean during the study period during non-intervention blocks, will form a control group and have medical record review only. *We request to waive consent for this record review only.* Clinicians and peripartum women participating in wireless physiologic monitoring will form the same participants for Aim 2, which will involve participant observation, record review, and retrieval of data from the wireless monitoring system and clinician responder phones. To complete Aim 3, We will perform semi-structured interviews on 30 clinicians and 30 postpartum women drawn from

¹ HIPAA: Health Insurance Portability and Accountability Act of 1996) is United States legislation that provides data privacy and security provisions for safeguarding medical information

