- Peripartum women:** To enable wireless monitoring to begin immediately or as soon as possible after cesarean delivery, the RA will approach *all* women waiting in labor or registering for delivery during the study period. Women cannot be approached prior to presentation for delivery due to logistical constraints with patient scheduling and follow-up in this setting. The RA will screen for eligibility and explain the study to eligible women and obtain assent for potential inclusion. Women will only be enrolled if the decision is made for an emergency cesarean

delivery during their labor or antepartum course. This decision will be made per the standard of care in the clinic and not influenced by research goals or procedures

In a private space, potential participants will have the study and study procedures described verbally in their preferred language (English or Runyankole) and given written information about the study in their preferred language. The RA recruiting and seeking consent will be carefully trained to fully explain the risks and benefits and to ensure women understand that they will still receive current standard of care at the hospital should they decline to participate in. Prior to describing the study and study procedures the RA will conduct a pain assessment using the facies and numerical pain scale and anxiety assessing using the State Trait Anxiety Scale (Appendix 10)

It will be clearly explained to women that actual enrollment will occur if the decision is made for an emergency cesarean delivery and that study explanation is being done ahead of time due to the due to the nature of childbirth with an unpredictable timing for a decision for emergency cesarean delivery, and often need for urgent medical care and the potential for a high level of emotional and physical stress at that time. For all women who provide assent, the RA will obtain written consent to study enrolment immediately after informed consent for the cesarean delivery has been obtained by the overseeing doctor performing the cesarean.

All consents will be translated into Runyankole and back translated to English. Consent forms will be read aloud in their entirety to potential participants. Women will be informed that participation is voluntary, there are no repercussions for not participating, and they can drop out at any point also without repercussion.

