Research assistants will be asked to document field notes at the time of consent to capture information on the length of time taken for the consent, if the participant had others present, and observations during the process of the consent (e.g. discussion by the participant with an attendant or family member)

If women are unconscious or in a mental state where they are unable to consent for themselves, an attendant or guardian will be approached for consent. As women in this condition are at high risk for morbidity and/or mortality inclusion in this study is key to achieve the objectives of reducing this risk. Additionally, women in this condition are the most likely to gain direct benefit from vital sign monitoring. As such if an attendant is not available the woman will be enrolled without consent to enable monitoring to begin immediately. Consent will be sought as soon as possible after the woman regains capacity to consent or an attendant becomes available. If the woman and/or her attendant declines to participate at that time all study procedures will be discontinued.

Study Procedures

1. A group meeting detailing the study background, procedures, risks and benefits will be held for all clinical providers in the department prior to study initiation.
2. We will obtain informed consent for clinicians and peripartum women admitted for delivery as described above.
3. A 2-hour training session on the use of the wireless monitoring system, nature of alerts and emergency mobile phone will be held for enrolled clinicians at a time convenient to them.
4. Alternative two-week blocks will be assigned to “intervention” vs “control”. During an “intervention block” all women delivering by emergency cesarean and consenting to participate will be monitored using the wireless device for the first 24 hours after delivery. During a “control

block" standard of care for monitoring will be used and women delivering via emergency cesarean will have record review only.

5. Maternity ward coverage schedules for enrolled specialist and midwives will be obtained. This will be used to determine the clinicians on call during each intervention block.
6. During the intervention block, midwives present in the theatre will be asked to perform the following tasks for any emergency cesarean deliveries s/he is present for:
 - a. Placement of the biosensor on any enrolled women s/he delivers by emergency cesarean delivery immediately after completion of the surgery.

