11. Every 24 hours a research assistant will perform medical chart review on enrolled participants to assess for documentation of the occurrence of any severe maternal outcome (Table 2). The research assistant will also review daily 24-hour reports generated by covering clinicians (standard maternity ward practice) to identify potential severe maternal outcomes not documented in the medical record.

Table 2: Severe Maternal Outcomes based on WHO Near Miss Criteria with demonstrated feasibility of collection in a RLS^{28,29,71}

Outcome	Definition/Measurement
Death	Mortality occurring at any time point after delivery and prior to discharge
Clinical based near-miss criteria	
Acute cyanosis	Blue or purple coloration of the skin or mucous membranes due to low oxygen saturation
Gasping	Terminal respiratory pattern, the breath is convulsively and audibly caught.
Severe bradypnea or tachypnea	Respiratory rate < 6 or Respiratory rate > 40
Shock	Persistent systolic BP ≤ 80 mmHg or a persistent systolic BP ≤ 90 mmHg with a HR ≥ 120.
Oliguria	Urinary output < 30 ml/hour for 4 hours or < 400 ml/24 hours non-responsive to fluids/diuretics.
Failure to form clots	Bedside clotting test or absence of clotting from the IV site after 7 minutes
Prolonged unconsciousness	Complete or near-complete lack of responsiveness to external stimuli.
Cardiac arrest	Sudden absence of pulse and loss of consciousness.
Stroke	Neurological deficit of cerebrovascular cause persisting ≥ 24 hours.
Uncontrollable fits	Refractory, persistent convulsions or status epilepticus.
Total paralysis	Complete or partial paralysis of both sides of the body.
Jaundice in the presence of pre-eclampsia	BP > 140/90) with proteinuria (> 1 + dipstick in ≥ 2 samples) and jaundice.
Laboratory-based near miss criteria	
Acute severe azotemia	Creatinine > 300 mmol/l or > 3,5 mg/dl
Severe acute hyperbilirubinemia	Bilirubin > 100 µmol/l or > 6.0 mg/dl.
Severe acute thrombocytopenia	<50 000 platelets/ml
Management-based near-miss criteria	
Use of continuous vasoactive drugs	Uninterrupted infusion of dopamine, epinephrine, or norepinephrine.
Hysterectomy	Surgical removal of the uterus following infection or hemorrhage.
Massive transfusion	Transfusion of ≥ 5 units of blood
Intubation and ventilation not related to anesthesia	Placement of an endotracheal tube or ventilation for > 60 minutes purposes other than anesthesia
Dialysis for acute renal failure	

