- Risk of additional clinical interventions or exams that may or may not be beneficial: Alerts of abnormal physiologic signs may prompt doctors to perform additional exams and clinical interventions. If abnormalities in physiologic signs do not correspond to developing or established clinical abnormalities this may mean additional procedures are performed without benefit. We will monitor for any substandard clinical care to participants, or participant distress caused by this and modify study protocols as necessary.
- Less than 24 hours between recruitment and consent: As noted above peripartum woman will be approached for recruitment into the study once admitted to the unit for delivery to allow monitoring to begin immediately after delivery. Due to this timeline, there will be less than 24 hours between initial approach and consent. Particularly given the high intensity time around childbirth, this exposes the women to some vulnerability in decision-making. The RA recruiting and seeking consent will be carefully trained to fully explain the risks and benefits and to ensure women understand that they will still receive current standard of care at the hospital should they decline to participate. Women indicating interest in participating will be approached again once the decision has been made for an emergency cesarean delivery. Due to potential unpredictable changes in clinical course and the development of complications that may render a woman unable to provide consent for herself, we have limited enrollment to those women who can either consent for themselves or who have a guardian available to consent for themselves. Consent via a guardian is included as monitoring critically ill women who may be unable to provide their own consent is paramount to ultimately affecting clinical outcomes

Both clinicians and peripartum women:

- Stress and anxiety related to study procedures: Post-graduate doctors may experience some stress and anxiety due to the requirement to hold the responder phone particularly given they

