### Exposure and Outcome Definitions

#### Aim 1 exposure

- Allocation arm
  - Intervention block group for all eligible participants during that “on block” (regardless of actual monitoring receipt i.e., intention-to-treat).

#### Aim 1

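### Protocol and SAP conflict on recording the primary outcome for intervention-block women who refuse: the ITT analysis counts them, but the protocol does not clearly allow their records to be reviewed

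*Protocol*

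**What the plan says.** **Protocol, Subject Enrollment and Consent Procedures (peripartum women).** For a woman unable to consent: "As such if an attendant is not available the woman will be enrolled without consent to enable monitoring to begin immediately". Consent is sought later, from her or from an attendant. On refusal: "If the woman and/or her attendant declines to participate at that time all study procedures will be discontinued". No exception is made for record review, and nothing is said about data already collected. Women in general are told that "they can drop out at any point also without repercussion".

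**Protocol, Study Procedures, item 11.** The primary outcome comes from this item: "Every 24 hours a research assistant will perform medical chart review on enrolled participants", with a check of the ward's 24-hour reports. The SAP sets the endpoint at hospital discharge.

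**Protocol, Study Intervention.** After describing the control group, who have medical record review only, the protocol states: "We request to waive consent for this record review only". The Study Population Overview table agrees: record review with consent for monitored women, and without consent for controls.

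**SAP, Aim 1 exposure and the Aim 1 analysis.** Women are assigned by block, "regardless of actual monitoring receipt i.e., intention-to-treat". The intervention group includes women who declined, were missed at screening, were screened but not enrolled, or were enrolled and never monitored. Event rates are to be calculated on all eligible women in each kind of period. The only note on missing data is a margin comment, and it concerns the control period.

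**A related inconsistency.** The Risk/Discomforts section says "we have limited enrollment to those women who can either consent for themselves or who have a guardian available to consent for themselves", and inclusion criterion 3 is to the same effect. Neither fits with enrolment when no attendant is available.

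**The concern.** An intention-to-treat comparison by block needs SMO status to discharge for every eligible woman, collected on the same footing in both arms. Read literally, the protocol ends SMO ascertainment when a woman enrolled under deferred consent, or her attendant, refuses. Control women are reviewed under a waiver and have no stated refusal route, so any resulting gap falls in the intervention arm only.

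Direction matters as well. Of women unable to consent, the protocol says: "As women in this condition are at high risk for morbidity and/or mortality inclusion in this study is key". If those who refuse carry more than average risk, then leaving them out, or treating them as event-free because no event was recorded, lowers the observed intervention rate and looks like benefit. The section on Monitoring and Quality Assurance excludes data that cannot be verified, so omission is a realistic outcome.

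The same lack of access affects women who decline at first approach. They are never enrolled, so item 11 does not cover them, and neither does the waiver, yet the SAP counts them.

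**Working it through.** **1. The plan's own figures (Protocol, Sample Size).** Inputs: 95 women per block, 13 blocks per arm, ICC 0.01, baseline SMO 13%, two-sided 0.05, 80% power, difference 5.7 points.
- Women per arm: 95 × 13 = 1,235.
- Effective n: 1,235 / (1 + 95 × 0.01) = 1,235 / 1.95 = 633.3. With the usual (95 − 1) it is 1,235 / 1.94 = 636.6. The stated 633 reproduces.
- Power, 13% v 18.7%, 633 per group: z = (0.057 × √633 − 1.96 × √(2 × 0.1585 × 0.8415)) / √(0.13 × 0.87 + 0.187 × 0.813) = (1.434 − 1.012) / 0.515 = 0.82, so power is 79.4%. The stated 80% reproduces, as an increase from 13%. For a decrease to 7.3% power is 92.0%, and the difference detectable at 80% is 4.8 points.

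These figures do not depend on the refusal clause. They serve only as the yardstick below.

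**2. Refusal after deferred consent.** The documents give neither the share lost, d, nor the SMO risk among those lost, r. Both are assumptions. Take a true rate of 13% in both arms.
- If the lost women are dropped: observed rate = (0.13 − d·r) / (1 − d).
- If they are scored event-free: observed rate = 0.13 − d·r.

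Shift in the intervention rate, in percentage points, when dropped:

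| d (women of 1,235) | r = 13% | r = 30% | r = 50% | r = 80% |
|---|---|---|---|---|
| 0.1% (about 1) | 0 | −0.02 | −0.04 | −0.07 |
| 0.5% (about 6) | 0 | −0.09 | −0.19 | −0.34 |
| 1% (about 12) | 0 | −0.17 | −0.37 | −0.68 |

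Worked corner: (0.13 − 0.01 × 0.80) / 0.99 = 0.122 / 0.99 = 12.32%, a shift of −0.68. Scored event-free, the same corner gives −0.01 × 0.80 = −0.8 points, but only if none of these women's events was recorded before refusal. Doubling d to 2% (about 25 women) gives −1.37 dropped and −1.6 event-free. If refusers carry less than average risk, dropping them shifts the rate the other way: with r = 0 and d = 1%, 0.13 / 0.99 = 13.13%, or +0.13.

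**3. Women who decline at first approach.** The protocol expects about 112 emergency cesareans per block and 85% consent. Over 13 blocks: 112 × 13 = 1,456, and 1,456 − 1,235 = 221 women whom the SAP counts but whom no stated consent or waiver covers. If the 1,235 have 13% SMO (160.55 expected events) and nothing is known of the 221:
- none has an SMO: 160.55 / 1,456 = 11.0%;
- all have one: (160.55 + 221) / 1,456 = 26.2%.

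These are bounds, not estimates. They run from 2.0 points below 13% to 13.2 above, so a bounding analysis alone cannot make up for having no record access to this group.

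**The case against.** The best reply is that the SAP plainly expects event data on decliners, so the investigators must have meant record review to go on. That is a fair reading of intent, and it is why this is a conflict to be resolved and not proof that data will be missing. But an expectation in the SAP does not authorise access that the protocol's waiver request does not cover.

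A reader might infer more than the documents support, in four ways.
- *That SMO data already recorded are lost.* The text stops procedures. It does not say that earlier data are discarded, and an event charted before refusal could be kept.
- *That any drop-out ends record review.* The statement on dropping out says nothing about records. Study Procedures item 17 samples women with under 24 hours of monitoring as enrolled participants, so stopping the monitor early is not in itself leaving the study. The consent forms, where withdrawal terms may appear, were not available for this review.
- *That the loss is large, say 2% to 10% of the arm.* Deferred-consent refusers must lack capacity, have no attendant present, and then refuse. Women admitted directly to ICU are excluded, and two other places in the protocol would not enrol such women at all. Nothing supports several per cent for this group.
- *That refusers are known to be sicker.* The high-risk wording describes women unable to consent. A woman refuses for herself only after regaining capacity, and one who dies or stays incapacitated with no attendant cannot refuse and is retained. Severity among refusers is an assumption.

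What stands is the conflict itself, its confinement to one arm, and the absence of any method for missing SMO there.

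**Conclusion.** The point holds as an unresolved conflict between protocol and SAP on outcome ascertainment in intervention blocks. Following the refusal rule literally leaves SMO follow-up after refusal missing in one arm, for women whom the ITT analysis must count.

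For deferred-consent refusers the likely effect is small: at most about 0.7 points if 0.1% to 1% of the arm is dropped, roughly an eighth of the planned difference (0.68 / 5.7 = 12%), and then only at an assumed 80% SMO risk. The direction favours the intervention only if refusers have above-average risk. The larger exposure is the roughly 221 expected initial decliners. The documents give no basis for the size or direction of any bias from them, but without record review the stated analysis cannot be carried out on that group.

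**What to change.** **Protocol, Subject Enrollment and Consent Procedures.** Limit what stops on refusal to the monitor, interviews and surveys. State that record review for SMO continues to discharge on the waiver terms requested for controls unless the woman explicitly objects, subject to ethics committee agreement. State whether data collected before refusal are kept.

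**Protocol, Study Intervention.** Extend the waiver request to record review for all eligible intervention-block women who decline, withdraw or are not enrolled, and word item 11 to match.

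**SAP, Aim 1.** Report the number with missing SMO by arm. Add a sensitivity analysis that counts those women as all having, then none having, an SMO.

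**Consistency.** Reconcile the deferred-consent paragraph with inclusion criterion 3 and the Risk/Discomforts section on enrolment without consent or a guardian.

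**Cost.** An amendment to protocol and consent wording, a wider waiver request, and a short SAP addition. Research assistants already do this chart review for controls under the same kind of waiver. The downside is that the committees must accept minimal-risk record review for women who declined monitoring. If they do not, the SAP should say that the ITT set cannot be fully observed and rely on the bounds.

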## Analysis Cohorts and Datasets

In the definitions below, a *cohort* refers to a particular set of participants and a *dataset* defines the time (or time intervals) contributed by participants in a cohort.

- **Screened cohort** – all participants with a screening CRF marked complete.
  - **Enrolled cohort** – subset of screened, who were eligible and enrolled i.e. received a study number
  - **Enrolled dataset** – analysis set of all baseline and follow-up data contributed by each participant in the enrolled cohort, regardless of compliance to group
- **Intervention cohort** – subset of enrolled cohort who are enrolled during an intervention time period
- **Control cohort** – subset of the enrolled cohort who were enrolled during the control block

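### The plan does not say that severe maternal outcomes are searched for on the same schedule and in the same sources for every woman analysed in both kinds of block

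*Protocol*

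**What the plan says.** **How outcomes are found.** Protocol Study Procedures item 11 states: "Every 24 hours a research assistant will perform medical chart review on enrolled participants". The next sentence adds the ward's routine daily reports, used "to identify potential severe maternal outcomes not documented in the medical record". That sentence names neither an arm nor an enrolment status.

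**What control women receive.** In the Aim 1 paragraph under Study Intervention, the women in non-intervention blocks "will form a control group and have medical record review only", and the consent waiver is requested for that review alone. Item 4 says of control blocks that "women delivering via emergency cesarean will have record review only". The Study Population Overview table agrees. None of these places gives a review frequency or mentions the 24-hour reports.

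**Who is enrolled.** The same Aim 1 paragraph says "We will also enroll 1235 women undergoing emergency cesarean delivery during the study period during intervention blocks". The consent section ties enrolment to written consent, and items 6, 8 and 9 speak of enrolled women as those wearing the sensor. The SAP (Analysis Cohorts and Datasets) instead defines the control cohort as a "subset of the enrolled cohort who were enrolled during the control block".

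**Who is analysed.** The SAP's Aim 1 analysis takes all eligible women in both kinds of period. It counts in the intervention arm those who declined, were missed at screening, or were screened but not enrolled. The SAP's Data sources list has chart review but not the 24-hour reports.

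**The concern.** By adding the second source, the protocol accepts that charts alone will miss some SMOs. If that source, or the daily review, is applied to one group and not the other, the primary outcome is measured with different sensitivity in the two groups. Intention-to-treat analysis and a GEE or mixed model for block clustering do not correct such a difference.

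The direction depends on which meaning of 'enrolled' the staff follow.

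- **Protocol usage.** Events found only in the reports would count mainly in intervention blocks. That works against the intervention: it shrinks a real benefit and can produce apparent harm. It would also feed into the DSMB's review for higher-than-expected SMO rates.
- **SAP usage.** Controls are covered, but intervention-block women who declined or were missed are analysed and still fall outside item 11. That gives a small bias the other way.

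Under neither meaning does item 11 cover everyone in the primary analysis.

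**Working it through.** **Inputs.** Protocol, Sample Size: 1,235 women per arm, 95 per block, ICC 0.01, effective size 633 per arm, control SMO rate 13%, detectable difference 5.7 points, two-sided 0.05, 80% power, 85% consent. Not in the documents: the share of SMOs missed without the fuller review. I assume 5, 10 or 20%.

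**1. The plan's own figure.** 1,235 / (1 + 95 × 0.01) = 1,235 / 1.95 = 633.3, which matches. (The usual 1 + (95 − 1) × 0.01 gives 636.6.) For power, with p̄ = (p₁ + p₂)/2:

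power = Φ{ [ |p₁ − p₂| − 1.96·√(2p̄(1 − p̄)/n) ] / √[(p₁(1 − p₁) + p₂(1 − p₂))/n] }

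With n = 633, 13% against 18.7% gives 79.4%, so the stated 80% corresponds to a 5.7-point increase. A fall of the same size, 13% against 7.3%, gives 92.0%. A fall is the effect hoped for, so 92% is the reference below.

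**2. Protocol usage of 'enrolled'.** Let s be the share of control SMOs detected, with full detection in the intervention arm. The observed control rate is 13% × s. Example, s = 0.90: the control rate is 11.7%, the intervention rate 7.3% and p̄ = 0.095. Power = Φ[(0.044 − 1.96 × 0.01648)/0.01644] = Φ(0.71) = 76.2%.

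With no true effect, the intervention arm shows 13% against 13% × s. The false-harm column is the chance of a significant result in that direction.

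| Control events missed | Observed difference, true fall of 5.7 points | Power | Apparent excess, no true effect | False harm |
|---|---|---|---|---|
| 0% | 5.7 | 92.0% | 0 | 2.5% |
| 5% | 5.05 | 85.6% | 0.65 | 5.3% |
| 10% | 4.4 | 76.2% | 1.3 | 10.4% |
| 20% | 3.1 | 49.3% | 2.6 | 30.1% |

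**3. Allowing for non-consenters.** About 15% of eligible intervention-block women (1 − 0.85) would not be enrolled but are analysed in that arm. If they get the control-type review, detection in the intervention arm is 0.85 + 0.15s. For s = 0.90 this is 0.985, so the observed rate is 7.3% × 0.985 = 7.19% and the difference 4.5 points.

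| Control events missed | Power, true fall of 5.7 points | False harm, no true effect |
|---|---|---|
| 5% | 86.4% | 4.8% |
| 10% | 78.4% | 8.7% |
| 20% | 55.2% | 23.3% |

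The gap is diluted but remains.

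**4. SAP usage of 'enrolled'.** Controls are fully covered and only the 15% non-consenters in intervention blocks get the lesser review. With no true effect, the intervention rate falls short by 13% × 0.15 × (0.05, 0.10, 0.20) = 0.10, 0.20 and 0.39 points. This is a small bias in favour of the intervention.

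**The case against.** A reader might infer that case-finding is in fact more sensitive in the intervention arm. The documents do not establish that, for these reasons.

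- The SAP counts controls as enrolled. The protocol's Sample Size section describes enrolment as running over 13 intervention and 13 control blocks.
- The sentence on the 24-hour reports is not limited to any arm, and the reports are ordinary ward practice.
- The Study Population Overview lists record review for both groups. The word 'only' for controls may simply exclude the device and the interviews. The table does not list the reports separately for monitored women either.
- Read literally, item 11 would leave controls with no specified SMO review at all. That cannot be intended, since SMO rates are required in both arms.
- Less frequent review need not lose events, because charts accumulate to discharge and components such as death, hysterectomy or massive transfusion are hard to miss.
- No figure in the documents supports any particular share of missed events.

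All of this stands against a claim of actual bias. It does not supply the missing statement. No sentence says that the same schedule and sources apply to every woman analysed. A source meant to hold what the medical record lacks fits poorly within a review limited to the medical record. The SAP does not restore parity, since it sets no schedule and does not list the reports. Even on the generous reading, unenrolled intervention-block women remain outside item 11.

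**Conclusion.** The point holds as a defect in the written plan: ascertainment of the primary outcome is not specified equally for all women analysed, and the two documents disagree on who is enrolled. Whether case-finding differed in practice cannot be told from them.

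If the protocol's usage is followed, the bias runs against the intervention. With 5–20% of control events missed, power for a true 5.7-point fall drops from 92% to between 86% and 49%, or between 86% and 55% with 15% non-consenters on control-type review. With no effect and 10% missed, the chance of false harm is about 9–10% instead of 2.5%. If the SAP's usage is followed, the bias is at most about 0.4 points the other way over the same range.

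These sizes rest on the assumed missed share, full detection elsewhere, and the protocol's 633 per arm and 13% rate. They show what could happen and do not estimate what did.

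**What to change.** - Reword item 11 so that the same chart-review schedule, the same form and the same search of the 24-hour reports apply to every eligible woman in intervention and control blocks, including intervention-block women who were not enrolled.
- Give 'enrolled' one meaning in the protocol and the SAP.
- Extend the record-review wording (Study Intervention, Study Population Overview, item 4) and the waiver request to cover the 24-hour reports.
- Add the reports to the SAP's Data sources.
- Record for each SMO whether it was found in the chart, the report or both, and add a sensitivity analysis using chart-identified SMOs only. This puts both arms on a common source and shows how much the reports contribute. It does not correct for a difference in how often charts were reviewed.

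The cost is some research-assistant time in control blocks, one field on the form and a short waiver amendment. The reports are already produced daily.
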